6.1.3 BASELINE

The baseline assessment is conducted by the IE, either online or in person. The IE will first review the e-consent in detail with the student and answer any questions. The IE will confirm that the student agrees with: (1) being randomized to one of two treatments; (2) the possibility of proceeding in an “adaptive” manner—ending treatment/going into maintenance or being randomized to one of two treatments for up to 8 additional weeks; (3) possibly participating in a group (if assigned to DBT); (4) completing assessments even if no longer in treatment; (5) providing information to create a unique identifier; and (6) having their therapy sessions video-recorded. After consent is obtained, questionnaire/interview baseline assessments will be conducted by the IE (see Table 1). At the end of this assessment or within 1 business day, student participants will receive confirmation of who their counselor will be and the date of their first teletherapy/in-person appointment (typically within 7 days after the baseline visit, but clinical concerns will take precedence). Students who decline participation prior to giving consent, or who enroll but later choose to withdraw from the study, will have access to the usual care at the CCC (Note: all randomized student participants will be included in the ITT analyses).

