6.1.4 RANDOMIZATION

Following the completion of the baseline assessment, the site PC will review the consent, document the randomization block variables (gender, medication, past suicide attempt), obtain randomization assignment from the Data Center at Duke University, and reveal randomization results to an already assigned counselor. Note that student participants will learn of their treatment assignment by the counselor at their first treatment visit (this procedure was used in the pilot project and received very favorably by students and counselors).

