9.3 CAMPUS TRIAL STATISTICAL ANALYSES

9.3.1 GENERAL APPROACH

Overview and Intent-to-Treat. The proposed trial design of adaptive treatment strategies (ATSSs) is like a factorial design;^{156,157,158,159} different analytic subgroups (see Table 8) are combined to answer different questions. Aim 1 is the trial's primary aim; Aims 2-5 are secondary aims and Aim 6 as an implementation aim. All student participants, once randomized, will be included in the intent-to-treat sample, and every effort will be made to collect all primary and secondary outcomes even if a student participant does not engage in randomly assigned treatments. The primary outcome of interest is suicidal risk, which includes suicidal ideation as well as suicide-related behaviors, such as non-suicidal self-injury (NSSI) and suicide attempts (SAs); however suicidal ideation is the primary DV due to relatively low rates of suicidal behaviors post-baseline with college students. Suicides will be tallied as well. All analyses allow for the inclusion of covariates listed as demographics and covariates in Section 8.1. Covariates will enter the model based in clinical importance (gender, age, current alcohol use, current substance use, etc.) and retained on a case-by-case basis based on statistical significance.

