Aim 2 analyses will contrast ATSSs beginning with CAMS vs. interventions beginning with TAU (i.e., to evaluate the main effect of initial treatment) on change (decrease) in suicide-related risk behaviors (SI, NSSI, and suicide attempts—the primary outcomes) from baseline to the end of Stage 2 (the primary contrast). This is a comparison of cells A+B+C vs. D+E+F (see Figure 2 and Table 8). Note that the primary continuous longitudinal outcome is assessed at baseline, mid-Stage 1 (3 weeks), post Stage 1 (6 weeks), mid-Stage 2 (10 weeks), post-Stage 2 (14 weeks) (end of acute treatment) and then again at 3-month follow-up (26 weeks), for a total of 6 measurement occasions. Linear mixed models¹⁶³ (LMM, also known as random effects or growth curve models), fit with SAS PROC MIXED will be used to analyze the longitudinal data. LMMs use all available measurements, allowing student participants to have an unequal number of observations and producing unbiased parameter estimates as long as unobserved values are missing at random. The analysis will fit a LMM with fixed effects for the intercept, time, group, and a group-by-time interaction term, where group is an indicator of phase-one treatment (CAMS vs. TAU as referent). The LMM will also include random effects for the intercept and time and an unstructured within-person correlation structure for the residual errors and will adjust for the following measures collected at baseline (pre-randomization): site, age, race, and clinical severity. Model diagnostics will be used to determine suitability of more parsimonious (e.g., autoregressive) correlation structures, and nonlinear (e.g., quadratic) effects for time. We do not expect the intervention effects to be attenuated due to counselor participants who are cross classified between the interventions. Nonetheless, we will assess the potential attenuation by assessing the counselor x intervention interaction. If significant, we will examine if the attenuation effect is limited to a select few counselors and eliminate as needed to remove potential counselor contamination of intervention effects. Counselor will be treated as a random effect which models potential correlation between student participants within a common counselor. If there is not sufficient variance, indicated by the reliability estimate of the random effect falling below 0.02 (a slighter lower threshold compared to

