supervision corresponding to the intervention will be tracked using logs of personnel time (and multiplied by corresponding wage and facility overhead rates). To make cost-effectiveness comparisons, incremental cost-effective ratios (ICERs) will be calculated as the incremental cost divided by the incremental clinical benefits (e.g., remission rate of suicide risk) for each pairwise comparison of intervention strategies. Uncertainty surrounding these estimates will be calculated as cost-effectiveness acceptability curves and confidence intervals, using bootstrapping with Monte Carlo simulations. In addition, we will conduct an exploratory analysis of the “hidden costs” to college campuses associated with not providing adequate treatment for students experiencing suicidal ideation and behaviors (e.g., crises on campus, NSSI in residence halls).

Aim 7 analyses focus on the experience of counselors in the study. Given the relatively small sample size, the fact that the same counselors will be administering all treatments, and no *a priori* hypotheses, we regard these analyses as exploratory. Counselors will be divided into clinically relevant groups based on cut-points on key demographic variables (e.g., age, gender, years of overall experience, years of *experience* treating suicidal students, etc.). Analyses of variance will be used to examine differences in continuous outcomes; logistic regression analyses and contingency table analyses will be used to analyze differences in dichotomous outcomes. we will also use effect size benchmarks and descriptive statistics to gauge potentially meaningful effects (e.g., eta-square > .06; odd ratios > 2.0).

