Aim 8 analyses focus on statistical contrast of the two randomized arms within Stage 1 and the two randomized arms within Stage 2. For Stage 1 comparisons, linear mixed models¹⁶³ (LMM, also known as random effects or growth curve models), fit with SAS PROC MIXED will be used to analyze the longitudinal data. LMMs use all available measurements, allowing student participants to have an unequal number of observations and producing unbiased parameter estimates if unobserved values are missing at random. The analysis will fit a LMM with fixed effects for the intercept, time, group, and a group-by-time interaction term, where group is an indicator of stage-one treatment (CAMS vs. TAU as referent). The LMM will also include random effects for the intercept and time and an unstructured within-person correlation structure for the residual errors and will adjust for the following measures collected at baseline (pre-randomization): site, age, race, and clinical severity. Model diagnostics will be used to determine suitability of more parsimonious (e.g., autoregressive) correlation structures, and nonlinear (e.g., quadratic) effects for time. Complexity of the model may be constrained by the available repeated measures. Counselor will be treated as a random effect which models potential correlation between student participants within a common counselor. If there is not sufficient variance, indicated by the reliability estimate of the random effect falling below 0.02 (a slighter lower threshold compared to Raudenbush and Bryk¹⁶⁴ (p.125), we will treat counselor as a fixed effect. The primary contrast is between groups’ difference in change from baseline to end of Stage 1. Comparison of these findings will be to the results from the linear contrasts of the components of the ATS as described in Aim 1.

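### Aim 2 allows counselors to be removed according to their observed treatment effect, with no criterion, cap or sensitivity label, despite the promise to analyse everyone randomised

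*Combined protocol and SAP*

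**What the plan says.** Section 9.3.2 describes Aim 2, the comparison of CAMS-first with TAU-first, as a linear mixed model. On counselors it begins: "We do not expect the intervention effects to be attenuated due to counselor participants who are cross classified between the interventions". It then says the counselor-by-intervention interaction will be assessed and that, if it is significant, the analysts will "examine if the attenuation effect is limited to a select few counselors and eliminate as needed to remove potential counselor contamination of intervention effects".

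The text gives no significance level for that test, no definition of an attenuated counselor and no limit on how many may go. It does not say whether the reduced analysis replaces the full one or sits beside it. The nearby reliability cut-off of 0.02 only decides whether counselor is a random or a fixed effect.

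Two other places commit to the full randomised set. Section 9.3.1: "All student participants, once randomized, will be included in the intent-to-treat sample". Section 6.1.3: "all randomized student participants will be included in the ITT analyses". Nothing reconciles these with the elimination step.

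On scope, section 9.3.1 states "Aims 2-5 are secondary aims and Aim 6 as an implementation aim". The Aim 1 text has no such step. Nor does Aim 8, which also compares CAMS with TAU (section 9.3.7: "Aim 8 analyses focus on statistical contrast of the two randomized arms within Stage 1"). Section 9.3.2 analyses the secondary longitudinal outcomes and Aim 3 with models resembling the Aim 2 model, without saying whether the step carries over.

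**The concern.** Removing a whole counselor does not in itself break randomisation. The site coordinator will "reveal randomization results to an already assigned counselor", so the counselor is fixed before allocation is known, and "the same counselors will be administering all treatments". Each remaining counselor still provides a randomised comparison.

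The harm lies in how counselors are selected. They would be removed because of the treatment effect seen in their own students, after a test on the same data. If attenuation means a smaller CAMS benefit, removal pushes the estimate toward CAMS. If it is judged against whichever sign the overall estimate has, there is no mean bias under no effect, but false positives rise more. Either way, the Aim 2 result would depend on an unspecified judgement made after outcomes are seen.

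**Working it through.** **Inputs from the documents.** 480 students, 240 per Stage 1 arm; Aim 2 effect 0.30 SD; two-sided level 2.5%; power 85%; SSI standard deviation 7 (all section 9.2). About 24 counselors at a time (section 5.1), up to 40 enrolled (section 1.1).

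**Assumptions, not in the documents.** Equal caseloads; 1:1 allocation within counselor; one standardised outcome; interaction tested at 5%; between-counselor SD of the true treatment effect from 0 to 0.3. The value 0.3 equals the whole planned effect.

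**The plan's own figure.** z = 0.30 × √(240/2) = 3.286. Power = Φ(3.286 − 2.241) = Φ(1.045) = 0.852, which agrees with the stated 85%.

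**How noisy one counselor's effect is.** With 24 counselors each has 480/24 = 20 students, 10 per arm. The sampling variance of one counselor's standardised effect is 2/10 = 0.20, so its SD is 0.45, larger than the effect sought. Even with a true between-counselor SD of 0.3, the real share of the observed variance is 0.09/(0.09 + 0.20) = 31%. At SD 0.2 it is 0.04/0.24 = 17%.

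**Simulation (400,000 trials per setting unless noted).** Each counselor's observed effect is the true mean, plus a counselor deviation, plus noise of variance 2/n, where n is students per arm (10 for 24 counselors, 6 for 40). If the interaction F test is significant at 5%, counselors are removed and the mean effect is re-tested at two-sided 2.5%, with the interaction pooled into the residual.

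- Reading A: attenuated means a smaller CAMS benefit. Reading B: smaller relative to the sign of the all-kept estimate.
- Upper version: drop the three most attenuated counselors whenever the test is significant. This skips the plan's check that the problem is confined to a few, and so leans high.
- Checked version: drop the fewest, at most three, and only if that makes the interaction non-significant.

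Overall false-positive rates with no true mean effect (pairs are upper / checked):

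| Counselors; SD of effect | Trials with elimination | All kept | Reading A | Reading B |
|---|---|---|---|---|
| 24; 0 | 5.0% / 4.8% | 2.5% | 3.2% / 2.7% | 4.1% / 2.9% |
| 24; 0.2 | 16% / 15% | 4.0% | 6.7% / 4.8% | 10.0% / 6.0% |
| 24; 0.3 | 37% / 31% | 6.0% | 12.5% / 8.1% | 21% / 11.6% |
| 40; 0 | not listed | 2.5% | 3.0% / 2.7% | 3.7% / 2.9% |
| 40; 0.3 | not listed | 4.4% | 7.6% / 5.4% | 12.0% / 7.2% |

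At SD 0.1 with 24 counselors (200,000 trials, upper version only) the rates are 3.9% under A and 5.3% under B, against 2.8% all kept.

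All-kept rates above 2.5% arise because this final test has no counselor-by-treatment random effect. That is a separate matter. With a counselor-level t-test, which holds 2.5% when all are kept, the upper version at 24 counselors and SD 0.3 gives 7.1% (A) and 12.0% (B). The rule therefore inflates error on its own, by less than the last column for that setting suggests.

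**Shift in the estimate, 24 counselors, reading A.** At SD 0, in trials where elimination happens: +0.13 / +0.06 SD, or 0.13 × 7 = 0.9 and 0.06 × 7 = 0.4 SSI points, against a planned 2. Averaged over all trials: +0.007 / +0.003 SD at SD 0, +0.022 / +0.010 at SD 0.2, +0.05 / +0.02 at SD 0.3. Under reading B the mean shift is zero.

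**Does it remove real contamination?** Let 3 of 24 counselors have zero effect and the other 21 an effect of 0.30. With all kept the expected estimate is 21/24 × 0.30 = 0.2625. The interaction test is significant in only 7.2% of trials. When three counselors are then dropped, on average 0.97 of them are truly contaminated, and in 26% of those trials none is. The estimate in trials with elimination is 0.397 / 0.329, above the uncontaminated 0.30. Over all trials it is 0.272 / 0.267, a recovery of about 0.009 / 0.004 out of a shortfall of 0.0375.

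**Power.** With a true effect of 0.30 and no counselor variation: 85.1% all kept, 85.8% / 85.6% with the rule.

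**The case against.** The strongest reply concerns weight and wording. Aim 2 is secondary, the Aim 1 and Aim 8 texts are free of the step, the plan does not expect attenuation, and a significant test is needed before anything happens. The verb has no stated object, and a reduced analysis run beside the full one would breach neither intention-to-treat statement. Two gates exist, significance and confinement to a few counselors, though neither is quantified. With no counselor variation and the checked version, false positives rise only to 2.7% or 2.9%, and the average shift is 0.003 SD. The large percentages need a counselor SD that has no source, a cap of three that is not in the plan and, in part, a final test that ignores counselor-by-treatment variation. The simulation also simplifies a six-occasion mixed model with attrition to one outcome with equal caseloads.

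Most of this stands and limits the size of the point. The figures at SD 0.3 should not carry it, and carry-over to Aim 3 and the secondary outcomes is only a possibility. It does not rescue the rule. The sentence names counselors and offers no modelling remedy, so removing them is the natural reading. Nothing says the full analysis remains the reported one. The inflation persists with a test that holds its level when everyone is kept. If something else was meant, the sentence still needs rewriting.

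**Conclusion.** The concern holds, and the rule is wrong as written. Followed on its natural reading, it produces an Aim 2 estimate selected on the outcome and conflicts with the commitment to analyse all randomised students. With 24 counselors and no counselor variation it acts in about 5% of trials. Under reading A it moves those estimates toward CAMS by 0.06 to 0.13 SD, and across both readings it raises overall false positives from 2.5% to between 2.7% and 4.1%. Larger inflation depends on real counselor differences, for which the documents give no figure. Averaged over all trials the shift is small. The step also fails at its stated purpose: in the 3-of-24 example it seldom acts, mostly picks the wrong counselors and recovers at most 0.01 SD on average. These sizes rest on equal caseloads, a 5% interaction test and removal of at most three counselors. The textual conflict does not depend on them. Because Aim 2 is secondary, this should be corrected but does not threaten the trial's primary analysis.

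**What to change.** In section 9.3.2, delete the elimination step. State that every randomised student stays in the Aim 2 analysis and that the counselor-by-intervention test is reported without action on it. Add that no elimination applies to the secondary outcomes or Aim 3.

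Any analysis excluding counselors should be a labelled sensitivity analysis, with criteria fixed in advance and defined without the outcome. Existing data can inform them: the Stage 1 CAMS adherence ratings (section 6.2.1) for CAMS cases, and the TAU Questionnaire (section 8.1) for TAU cases only, bearing in mind that counselors complete it themselves. A random counselor-by-treatment effect is a separate, optional change with some power cost; this correction does not depend on it.

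The cost is wording only. No new data are needed, and the stated 2.5% level and 85% power are unaffected. The downside is that real contamination leaves the Aim 2 estimate diluted, as intention-to-treat implies: 0.26 instead of 0.30 SD in the 3-of-24 example.

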Notes (2): \$For all assessments collected as part of an Independent Evaluator (IE) visit (i.e., those assessments not collected specifically at treatment visits), there will be a +/-1 week window around the scheduled assessment date for purposes of data collection. IE assessments collected outside of this window will still be collected and values will be imputed based on when the assessment should have occurred.																
Notes (3): *These measures are exclusively collected in the Titanium electronic medical record and will be exported at regular intervals throughout the study period.																

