4.2 OVERALL DESIGN

As shown in Figure 1 (on page 9), the proposed multisite SMART will involve randomization at two stages. At Stage 1, all student participants ($N = 480$) will be randomized to 4-6 weeks of CAMS or TAU. Beginning at session 4, the counselor will rate the student participant in terms of clinical response. Insufficient responders (e.g., non-responders) to Stage 1 will be re-randomized to one of two Stage 2 treatments for an additional 1-8 weeks: 1) CAMS (either continued or for the first time) or 2) CC-DBT.

Thus, four ATSSs are possible:

- ATS-1: Start with CAMS, if responding, enter maintenance treatment; if not, continue with CAMS;
- ATS-2: Start with CAMS, if responding, enter maintenance treatment; if not, switch to CC-DBT;
- ATS-3: Start with TAU, if responding, enter maintenance treatment; if not, switch to CAMS;
- ATS-4: Start with TAU, if responding, enter maintenance treatment; if not, switch to CC-DBT.

Our pilot showed at Stage 1, 48% and 44% treatment response rates across CAMS and TAU, with 27% and 17% attrition rates, respectively—differences not statistically significant. Based on these findings, we assume an equal response rate of 50% across both Stage 1 treatments (CAMS and TAU), leaving $N=240$ participants eligible for Stage 2 treatments. Treatment responders at the end of Stage 1 will end study treatment and enter maintenance, which includes monthly monitoring and continued assessments with the IEs. All student participants will complete weekly measures as part of treatment. Research assessments by independent evaluators (IEs) will be conducted at baseline, mid-Stage 1 (Week 3), end of Stage 1 (Week 6), mid-Stage 2 (Week 10), end of Stage 2 (Week 14), and at 3-month follow-up (Week 26).

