4.4 JUSTIFICATION FOR INTERVENTION

First Stage (Stage 1) of SMART Study (N=480): Randomization to TAU or CAMS (4-6 Weeks). After baseline, student participants will be randomly assigned to TAU (n= 240) or CAMS (n=240). Stage 1 treatment will last 4-6 weeks. We chose this treatment length because the average number of sessions at CCCs is 5.22 (with a median of 4 sessions),²¹ 6-8 CAMS sessions were enough to resolve SR in college students in an earlier trial,²⁷ and in our CAMPUS feasibility study, average number of Stage 1 sessions was 6. Student participants who appear to be deteriorating (worsening SI on the Counselor CGI-I scale) or who maintain high levels of SI without improvement may be re-randomized to Stage 2 early after session 4.

Student participants randomly assigned to TAU will receive the customary treatment they would receive at that CCC—on average, weekly individual therapy, but it may also occasionally include group participation and/or medication referral. Counselors conducting TAU treatment will be informed to do counseling as usual for a period of 4-6 weeks, except that counselors will be asked not to utilize CAMS or DBT strategies. The book entitled *“Collaborative Assessment and Management of Suicidality: Managing Suicidal Risk: A Collaborative Approach (2nd edition)”*⁷ will serve as the manual for CAMS treatment in Stage 1/Stage 2. CAMS individual sessions will be provided weekly for 50-60 minutes and will follow the Suicide Status Form.

Second Stage (Stage 2) of SMART Study (n≈240): Re-randomization to CC-DBT or CAMS (1-8 Weeks). The treatment length for Stage 2 was chosen based on previous studies with CAMS and DBT, ease of dissemination to CCCs later, and informed by data from the CAMPUS feasibility study. Based on previous CAMS studies,²⁷ our pilot study and CAMPUS feasibility study, we estimate that n≈240 of student participants will resolve their SR during Stage 1 and that n≈240 will be re-randomized to Stage 2.

DBT Individual Therapy. Participants will receive weekly individual teletherapy/in-person sessions with a CC-DBT-trained counselor for up to 8 weeks total. The DBT manual²⁹ guidelines such as orienting clients to the treatment model, using a diary card to monitor problematic behaviors, relying on a hierarchy of targets to guide treatment at each session, and conducting chain and solution analyses to determine and address controlling variables of problematic behavior will be followed.¹⁴⁵

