Raudenbush and Bryk¹⁶⁴ (p.125), we will treat counselor as a fixed effect. The primary contrast is between groups' difference in change from baseline to month 6 (end of acute treatment through Stage 1 and Stage 2 active treatment). The follow-up contrast at week 26 (12 weeks post-acute treatment) will also be examined in this and in all subsequent analyses. LMMs like the above for the primary outcome will be run for the secondary longitudinal outcomes: CAMS vs. TAU on CCAPS subscales (Depression, Anxiety, Academic Distress, Overall Distress), CGI-I and CGI-S (measured by IE), and cumulative GPA.

AIM 3 analyses will examine the relative effectiveness of switching to a more comprehensive suicide-focused treatment approach (e.g., CC-DBT) among those who do not respond sufficiently to Stage 1 treatments vs. a less intensive suicide-focused approach (e.g., CAMS). This analysis is a comparison of cells C+F (switch to CC-DBT) vs. B+E (switch or continue with CAMS) in Table 8. Both primary and secondary longitudinal outcomes outlined above will be examined using an LMM like that described above, but (a) including only the subset of responders to Phase 1 treatment, (b) defining group as switching to CC-DBT (cells C+F) vs. continuing or switching to CAMS (cells B+E), and (c) using monthly longitudinal outcomes from week 4 to week 24 (7 measurement occasions).

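### Aim 3's analysis window (weeks 4 to 24, seven occasions) does not fit the assessment schedule, and its population clause names the wrong group; the Aim 2 end-point label and one power input need minor date corrections

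*Combined protocol and SAP*

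**What the plan says.** **Schedule.** Section 4.2 lists evaluator assessments at baseline, weeks 3, 6 and 10, then "end of Stage 2 (Week 14), and at 3-month follow-up (Week 26"). The Aim 2 text in 9.3.2 gives the same six occasions, ending "post-Stage 2 (14 weeks) (end of acute treatment) and then again at 3-month follow-up (26 weeks"). The notes to Table 1 (section 1.3) add that for evaluator visits "there will be a +/-1 week window around the scheduled assessment date for purposes of data collection". The synopsis sets total participation at 26 weeks.

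**Aim 3 (9.3.2).** The comparison is cells C+F (CC-DBT) against B+E (CAMS). The model is to (a) include only responders to the first-phase treatment, (b) define group by those cells, and (c) proceed "using monthly longitudinal outcomes from week 4 to week 24 (7 measurement occasions"). It covers the primary and the secondary longitudinal outcomes. Shortly before, the Aim 2 text says: "The follow-up contrast at week 26 (12 weeks post-acute treatment) will also be examined in this and in all subsequent analyses".

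**Aim 2 (9.3.2).** The opening sentence defines the change as running "from baseline to the end of Stage 2 (the primary contrast"). The later sentence that states the contrast calls it the "difference in change from baseline to month 6 (end of acute treatment through Stage 1 and Stage 2 active treatment").

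**Power for Aim 2 (9.2).** The 85% figure rests on a two-sided t-test at 2.5%, 240 per arm and d = 0.30. The text then mentions a baseline to week 26 correlation of up to 0.40 from pilot data. For the 3-month follow-up it states 94% power, assuming a baseline to 48-week correlation of 0.3.

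**The concern.** Aim 3 is the only stated test of whether stepping up to CC-DBT helps students who did not respond in Stage 1. Its clause asks for a monthly series that the trial does not collect and a count of occasions that the evaluator visits cannot supply. It also names a population that is not in the compared cells. Analysts would have to choose the visits, the starting point and the treatment of week 26 themselves, possibly after seeing data. The moderation analyses within Stage 2 (9.3.3, Aim 5) extend these outcome models, so the gap carries over to them.

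The Aim 2 label matters less. It puts the date of the follow-up visit in the sentence that states the primary contrast of that aim. The 48-week input names a time at which nobody is assessed.

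**Working it through.** **1. The plan's own figure.** Inputs from 9.2: n = 240 per arm, d = 0.30, two-sided alpha 0.025 (critical z = 2.241).
- Noncentrality = 0.30 × √(240/2) = 3.286.
- Power ≈ Φ(3.286 − 2.241) = 0.852; with the noncentral t, 0.850.
- The stated 85% is reproduced. It uses no visit date and no correlation, so the date corrections leave it unchanged.

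**2. Aim 3 window, evaluator-rated outcomes.** Schedule {0, 3, 6, 10, 14, 26}; window 4 to 24.
- Nominal dates: {6, 10, 14}, which is 3 visits.
- With the one-week allowance: 3 + 1 = 4, so the week 3 visit can just enter, giving at most 4. Week 26 can be held no earlier than 26 − 1 = 25, so it stays outside.
- Taking monthly as four-weekly: 4, 8, 12, 16, 20, 24 is 6 points, not 7. Seven points would need a spacing of 20/6 = 3.33 weeks, or a start at week 0.

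**3. Aim 3 window, CCAPS.** Section 8.1 has the CCAPS collected at every session as well as at the assessments. With weekly sessions on the nominal schedule, weeks 4 to 14 can give up to 14 − 4 + 1 = 11 values. The count therefore differs from the SSI, but this is not a monthly series from week 4 to week 24 either.

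**4. Aim 3 population.** In Table 8 the responder cells are A and D. The compared cells are B, C, E and F, all insufficient responders. The overlap of {A, D} with {B, C, E, F} is empty, so clause (a) taken literally leaves nobody in the model. The sizing for Aim 3 in 9.2 and the Stage 2 part of Aim 8 in 9.3.7 both use the insufficient responders.

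**5. Starting point.** Re-randomization has no fixed week. Under 4.4, some participants "may be re-randomized to Stage 2 early after session 4", which can fall before week 6. The synopsis and 6.1.6 let treatment pause over academic breaks, so it can also fall later. No single count of occasions after re-randomization holds for everyone.

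**6. Aim 2 label.** Six months = 6 × 365.25/(12 × 7) = 26.1 weeks. The next sentence of the plan places week 26 at 12 weeks after acute treatment, so acute treatment ends at 26 − 12 = week 14 (3.2 months). The label is 12 weeks late.

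**7. Power text.** 48 − 26 = 22 weeks after the last assessment. No formula is given for the 94%, so the variance factor f is an assumption here. Power = Φ(3.286/√f − z), with rho = 0.3:

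| Assumed form | f | Two-sided alpha | Power |
|---|---|---|---|
| baseline-adjusted, 1 − rho² | 0.91 | 2.5% | 88.6% |
| 1 − rho | 0.70 | 2.5% | 95.4% |
| change score, 2(1 − rho) | 1.40 | 2.5% | 70.4% |
| baseline-adjusted, 1 − rho² | 0.91 | 5% | 93.1% |

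The stated 94% lies inside this range.

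**The case against.** **Aim 2.** A reader might infer that the time point is open between weeks 14 and 26, or that there are two primary tests. The documents do not support that. The bracket, the opening definition, the visit list and the separate follow-up contrast all leave only week 14. This objection stands, so the label is an editorial correction.

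**Seven occasions.** A reader might infer that no outcome could give seven values in the window. That is too strong, because the CCAPS is taken at every session. The shortfall applies to evaluator-rated outcomes, which include the primary SSI. A count of seven might have come from Table 1, whose layout cannot be read reliably here. Any count that includes baseline and week 26 is in any case not a count within weeks 4 to 24.

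**Week 26.** The rule that it will also be examined can be read as adding it to the Aim 3 window. That is a fair reading. It settles that week 26 is wanted, but the window as printed still omits it.

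**Power.** A reader might infer that 0.40 and 0.3 contradict each other, or that 94% is wrong. Neither follows. The first is an upper value from pilot data and the second is a planning assumption, and the method behind the 94% is not stated.

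**Weight.** Section 9.3.1 makes Aims 2 and 3 secondary. That is correct and limits the consequence.

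**Conclusion.** The point holds, mainly for Aim 3. For the SSI and other evaluator-rated outcomes the window contains 3 assessments, at most 4, against the 7 stated. It omits week 26, and the population clause excludes every participant in the compared cells. This should be fixed before analysis.

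The Aim 2 label (12 weeks late) and the 48-week input (22 weeks past the last visit) are minor corrections. Nothing here changes Aim 1, N = 480 or the 85% power.

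The conclusion rests on the six assessments listed in 4.2 and 9.3.2 and on the one-week allowance in 1.3. The amendment log records a change to 14 weeks of treatment and 26 weeks in total, so the odd dates may be left over from a longer design. That is an inference, and the finding does not depend on it.

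**What to change.** **Section 9.3.2, Aim 3.**
- Replace the window and count with the scheduled assessments that the model will use, including week 26. State separately how the session-level CCAPS values enter.
- State the starting point. Stage 2 re-randomization, as the Stage 2 contrast of Aim 8 in 9.3.7 already uses, is one option. If it is chosen, do not fix a number of occasions, and say how assessments are handled when re-randomization falls before or after week 6.
- In clause (a), change responders to insufficient responders, to agree with cells C+F against B+E.

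**Section 9.3.2, Aim 2.** Replace month 6 with week 14 (end of Stage 2), and keep week 26 as the follow-up contrast.

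**Section 9.2, Aim 2.** Replace 48-week with 26-week. State the interval over which the pilot correlation of up to 0.40 was measured, and give the formula behind the 94%.

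**Cost.** Wording in two sections, one small analysis decision (the Aim 3 starting point, best made before outcome data are examined), and a restatement of the follow-up power with its method. Sample size, visits and model type do not change.
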